Title: Prophylactic antibiotic use in transarterial chemoembolization for hepatocellular carcinoma: an open-label, randomised, prospective study

Introduction:

Liver cancer especially hepatocellular carcinoma (HCC) is among the top five most common carcinomas in the world [1]. The treatment options for HCC includes surgery, liver transplantation, and radiofrequency ablation (RFA) with good survival rates. However, most HCC patients have angioinvasion. Furthermore, multiple lesions cannot be treated with such treatment strategies [2]. Image-guided transarterial chemoembolization (TACE) is accepted worldwide as a standard of care treatment for patients with hepatocellular carcinoma (HCC) in intermediate stage and good performance status [3]. TACE procedures, performed by the interventional radiologists, are minimally invasive with excellent outcomes as part of the nonsurgical treatment of HCC [1, 4]. Post-procedure-infection is uncommon but can lead to liver abscess and prolonged hospital stay. [7, 8] The chances of post-procedure-infection are higher in patients taking anticancer drugs due to immunosupression. [5, 6]. Incidence of liver abscess after TACE is 0.1 - 4.5% but carries a mortality rate of up to 50% [7, 8, 9].

TACE was linked to a risk of liver abscess. Prophylactic antibiotics pre-procedure lower this risk and ensuing surgical intervention [6]. Prophylactic antibiotics may not be required in TACE for HCC patients [10, 11, 12]. Moreover, old age, compromised hepatic function, hypoalbuminemia, portal vein cancer embolus, invasive procedures, using broad-spectrum antibiotics, and having diabetes mellitus are the independent risk factors for hospital-acquired infections (HAIs) after TACE in patients with primary liver cancer [1, 13].

According to the latest Cardiovascular and Interventional Radiological Society of Europe (CIRSE) standards of practice guidelines (2021), routine antibiotic prophylaxis is not recommended [14]. However, prophylactic antibiotics are recommended in cases where there is a high risk of developing a liver abscess. These include biliary obstruction or the presence of a bilioenteric anastomosis. The choice of agent is dependent on the suspected path ogens (upper gastrointestinal tract flora) and consideration should be given to potential hepatotoxicity of each agent. In complex cases involving multiple organisms, antibiotic resistance, or allergies, consulting with a microbiologist may be beneficial [14].

To date, it is uncertain whether the use of antibiotics as prophylaxis before TACE is beneficial or not in the prevention of postoperative infection.

Excessive antibiotic use is a global problem and carries risks of adverse drug reactions like allergy or anaphylaxis, increased cost, and contributes to the emergence antimicrobial resistance [15, 16]. Therefore, it is the need of the hour to explore the utility of prophylactic antibiotics in TACE.

This study aims to determine the effectiveness of prophylactic antibiotic use for TACE and occurrence of postoperative liver abscess.

Methods

Inclusion Criteria:

- 1. Age 18 65 years
- 2. Diagnosis of primary liver cancer or hepatocellular carcinoma
- 3. Patients receiving TACE in PKLI & RC

Exclusion Criteria:

- 1. Receiving two or more TACE during the same hospitalization
- 2. Use of any antibiotics other than the prophylactic antibiotic in 48hours prior to TACE
- 3. Known hypersensitivity to specified antibiotic used in the study
- 4. Incomplete or missing laboratory investigations and data
- 5. Taking Sorafenib before TACE
- 6. TACE combined with ablation or immunetherapy
- 7. Tumor size >10 cm
- 8. Portal vein thrombosis
- 9. Dilated biliary channels on CT scan / Billiary invasion by tumor

Study Outcomes:

- 1. Predominantly neutrophilic leukocytosis ($> 11 \times 10^9$ /L) with fever (> 38 °C) in upto 48 hours post-TACE
- 2. Occurrence of liver abscess as diagnosed by imaging within 30 days of the procedure

3. Liver abscess requiring an intervention (e.g., percutaneous transhepatic abscess drainage (PTAD), percutaneous transhepatic abscess puncture or liver abscess incision) within 30 days of TACE

Sampling Technique:

In this study, consecutive sampling technique and randomization by lottery method will be applied. In lottery method the investigator will randomly draw numbers from the box to choose sample until the final sample size reaches. Two numbers will be assigned as '1' for antibiotic group and '2' for no antibiotic group.

Current standard of care treatment at PKLI&RC (as per local guidelines) would be given to all patients receiving TACE for the intervention group or 'antibiotic group' (i.e., Inj. Ceftriaxone 1g, intravenous × stat). While no antibiotic would be given to the 'no antibiotic group'.

Statistical analysis:

- 1. Data to be recorded on Excel sheet and subsequently exported to SPSS version 24 for further analysis.
- 2. A univariate analysis will be employed for the comparison of variations in patients' baseline characteristics between the preventive medication group and the nonpreventive medication group. The Student's t-test will be employed to evaluate if the obtained data had a homogeneous variance and a normal distribution. For nonhomogeneous variance, the comparisons were made using a one-way analysis of variance (ANOVA). In order to compare categorical variables, Fisher's exact test or Pearson's 2 test was used as applicable.
- 3. The univariate analysis included chi-square tests for categorical variables and t-tests for continuous variables. Significant variables (P < 0.01) in univariate analysis and covariates considered clinically influential were then analyzed by multivariate stepwise logistic regression (forward stepwise logistic regression) to identify significant variables. We applied univariate and multivariate logistic regression models to estimate odds ratios (ORs) with 95% confidence intervals (CIs) for significant

- variables for finding potential risk factors in WBC> 11×10^9 /L group or postoperative infection group.
- 4. *P* value less than 0.05 was considered statistically significant.

References:

- Li B. Prophylactic Use of Antibiotics for Postsurgical Infection in c-TACE and DEB-TACE High-Risk Patients: A Case-Control Study. Journal of Healthcare Engineering. 2022 Apr 11;2022.

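### Reactions to the antibiotic are one of the stated reasons for the trial, but no outcome or planned analysis records a reaction to the study ceftriaxone dose

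*Combined protocol and SAP*

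**What the plan says.** The closing paragraphs of the Introduction give two reasons for the trial. The first is doubt about benefit: "it is uncertain whether the use of antibiotics as prophylaxis before TACE is beneficial or not in the prevention of postoperative infection". The second is harm: excessive antibiotic use "carries risks of adverse drug reactions like allergy or anaphylaxis, increased cost, and contributes to the emergence antimicrobial resistance". The sentence that follows draws the inference: "Therefore, it is the need of the hour to explore the utility of prophylactic antibiotics in TACE". The stated aim is narrower than that inference: "This study aims to determine the effectiveness of prophylactic antibiotic use for TACE and occurrence of postoperative liver abscess".

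Methods, Study Outcomes, lists three items:
- Item 1 is an early infection marker: "Predominantly neutrophilic leukocytosis" above a stated count, together with fever, "in upto 48 hours post-TACE".
- Item 2 is "Occurrence of liver abscess as diagnosed by imaging within 30 days of the procedure".
- Item 3 is an abscess that needs an intervention, over the same 30 days.

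Under Sampling Technique, one arm receives a single intravenous ceftriaxone dose, described as current local standard of care, and the other receives no antibiotic. Exclusion criterion 3 removes patients already known to be hypersensitive to the study antibiotic. The Statistical analysis section covers baseline comparisons and a search for risk factors for a raised white cell count or postoperative infection.

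**The concern.** The comparison is ceftriaxone against nothing. The question of use is therefore a trade: infections prevented against reactions caused, and only one arm is exposed to the study drug. The plan measures one side of that trade.

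An anaphylactic reaction to the study dose would fall under no listed outcome and into no planned table. The plan does not forbid reporting it, but nothing ensures that reactions are looked for, recorded in a uniform way or counted by arm. If the trial then found fewer infections with ceftriaxone, readers could not learn from it what reactions accompanied that gain, although the protocol itself raises the question.

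**Working it through.** The plan states no figure on this point, so there is none to reproduce. The main check sets the sections side by side.

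**Step 1. Harms named in the Introduction against what is collected**

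| Harm named | Study Outcome that records it | Planned analysis |
|---|---|---|
| Allergy or anaphylaxis | none of 3 | none |
| Cost | none of 3 | none |
| Antimicrobial resistance | none of 3 | none |

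Outcome 1 does not stand in for a drug reaction. It is framed as an infection marker and requires fever together with neutrophilic leukocytosis.

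**Step 2. Could another section capture a reaction?**

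- Exclusion criterion 3 works at entry and only on known hypersensitivity. A first reaction happens after entry.
- Exclusion criterion 4 removes patients with incomplete or missing laboratory investigations and data, and inclusion criterion 3 requires that TACE is received. If a reaction to a dose given before the procedure led to TACE being deferred or tests being missed, that patient could drop out of the dataset. A safety count therefore has to cover every randomised patient who received the dose.
- The Statistical analysis section contains no safety item.

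**Step 3. What would recording reactions deliver?**

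The documents give neither a sample size nor a reaction rate. The values of n (ceftriaxone recipients) and p (true reaction rate) below are assumptions, shown as a range.

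- If no reaction is seen among n recipients, the exact two-sided 95% interval runs from 0 to 1 − 0.025^(1/n).
- The chance of seeing at least one reaction is 1 − (1 − p)^n.

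| n | Upper limit if none seen | Chance of at least one, p = 1% | Chance of at least one, p = 0.1% |
|---|---|---|---|
| 50 | 7.1% | 39.5% | 4.9% |
| 100 | 3.6% | 63.4% | 9.5% |
| 200 | 1.8% | 86.6% | 18.1% |
| 500 | 0.7% | 99.3% | 39.4% |

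For n = 100: 1 − 0.025^(1/100) = 0.0362, and 1 − 0.99^100 = 0.634.

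A count with its interval thus bounds the reaction rate at any of these sizes. A reaction as rare as 1 in 1,000 would more often than not go unseen even among 500 recipients. Description is feasible, but a powered comparison of rare reactions is not to be expected.

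**The case against.** The stated aim is effectiveness and abscess, and the outcomes serve that aim. Harm is only one of two reasons given, and the sentence on harm speaks of excessive antibiotic use in general, not of this dose. Ceftriaxone is local standard of care, so the departure from practice is withholding it, and the outcomes measure the risk of doing so. If no benefit appears, accepted harms already argue against routine use without being measured again. The proposed count would be imprecise, and cost and resistance would still go unmeasured. Consent pages are not part of the text available, so safety reporting described there cannot be ruled out.

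Much of this stands. The gap lies between rationale and outcomes and is not a failure of the stated aim. It matters mainly if a benefit is found. But none of it supplies a place where a first reaction is recorded, and safety reporting described elsewhere would not make reactions an outcome or a planned analysis. Imprecision is a reason to report descriptively, not a reason to leave reactions uncounted.

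A reader might infer three stronger things that the documents do not support:

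- **That the antibiotic arm can only look equal or better.** It can do worse on every outcome, by chance or in truth. The Introduction itself lists use of broad-spectrum antibiotics among the risk factors for hospital-acquired infection after TACE, and no test is stated to be one-sided.
- **That liver toxicity is part of the trial's rationale.** The remark that "consideration should be given to potential hepatotoxicity of each agent" belongs to a summary of guideline advice on choosing an agent, directly after a discussion of high-risk biliary cases.
- **That reactions would rival the abscesses prevented.** The documents give an abscess incidence of 0.1–4.5% but no reaction rate and no expected effect of prophylaxis. Any such balance would rest on assumed rates, and it would set reactions of any severity against an event with a quoted mortality of up to 50%.

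**Conclusion.** The point holds in a limited form. Drug reactions are offered as one reason for exploring utility, yet 0 of 3 outcomes and 0 planned analyses record a reaction to the study dose. Followed as written, the plan yields infection results by arm and no harm data by arm. It would go too far to say that the trial can conclude nothing about utility: a result showing no benefit would still inform practice. What it cannot do is accompany a finding of benefit with an account of the reactions.

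The conclusion rests on reading the sections and on no assumed rate. The size of the harm that goes unrecorded cannot be estimated from the documents. The table under step 3 depends on assumed n and p and shows only what recording could deliver. This should be corrected, but it does not undermine the infection comparison.

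**What to change.** Add a fourth, descriptive item to Study Outcomes with two parts:

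1. Any suspected allergic or anaphylactic reaction to the study ceftriaxone dose within 48 hours of the dose, including in randomised patients whose TACE is deferred or whose laboratory data are incomplete.
2. Any serious adverse event within 30 days, in both arms.

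Add to Statistical analysis: counts by randomised arm; an exact 95% confidence interval for the reaction rate in the antibiotic arm; no hypothesis test; and a statement that the trial is not sized to compare rare reactions. Present this table beside the infection results when concluding on utility, and say there that cost and resistance were not measured.

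The cost is a few fields on the data sheet and one table. The 48-hour and 30-day windows match those already set for the infection outcomes, although the documents give no visit schedule, so the sponsor should confirm that patients are contacted at those times. The downsides are a little more data entry and, because the trial is open-label, possible reporting bias for mild reactions, which should be stated as a limitation.

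### A bilioenteric anastomosis, named in the Introduction as an example of high liver-abscess risk, is covered by no eligibility or allocation rule, so such a patient can be randomised to no antibiotic

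*Combined protocol and SAP*

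**What the plan says.** The Introduction summarises the 2021 CIRSE standards of practice. Routine prophylaxis is not advised, but "prophylactic antibiotics are recommended in cases where there is a high risk of developing a liver abscess". Examples follow: "These include biliary obstruction or the presence of a bilioenteric anastomosis".

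The Methods list 3 inclusion and 9 exclusion criteria. Entry is broad; inclusion 3 reads "Patients receiving TACE in PKLI & RC". One criterion, exclusion 9, concerns the biliary tract: "Dilated biliary channels on CT scan / Billiary invasion by tumor".

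Under Sampling Technique, "consecutive sampling technique and randomization by lottery method will be applied". A draw of 1 means a single intravenous dose of ceftriaxone 1 g, and a draw of 2 means no antibiotic. No exception for high-risk patients is stated.

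The rationale, at the end of the Introduction, is that "it is uncertain whether the use of antibiotics as prophylaxis before TACE is beneficial or not in the prevention of postoperative infection".

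**The concern.** The protocol cites a recommendation to give prophylaxis to high-risk patients and names two kinds of such patient. Its exclusions match one kind and are silent on the other. Under the written rules, a patient of the second kind can be randomised away from prophylaxis in a situation where the protocol's own cited source recommends it.

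The trial's rationale does not clearly extend to these patients. The uncertainty it states is about prophylaxis before TACE in general. Nothing in the documents says that the recommendation is in doubt for patients with an anastomosis, or that enrolling them is intended.

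What is at stake is the safety of individual patients. The Introduction gives liver abscess a mortality of up to 50%. That figure is for abscess after TACE in general and is not specific to patients with an anastomosis, but it shows that the outcome in question is a serious one.

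**Working it through.** No arithmetic applies beyond a count. The documents give no sample size, allocation ratio or number of patients with an anastomosis, so there is no figure to reproduce and no probability to compute. The check is to set the Introduction's two examples against every rule that decides who is randomised and what they receive.

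**1. The two examples against the exclusions**

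| High-risk example in the Introduction | Matching rule in the Methods |
|---|---|
| Biliary obstruction | Exclusion 9, by proxy: dilated ducts on CT, or tumour invasion of the biliary tract |
| Bilioenteric anastomosis | None |

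The Introduction lists the two as alternatives, so a rule for the first cannot be read as covering the second.

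**2. All eligibility criteria (3 + 9 = 12)**

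- Inclusions 1 to 3 concern age, diagnosis and receiving TACE at the centre. None restricts biliary surgical history.
- Exclusions 1, 5 and 6 concern repeat TACE in one admission, prior sorafenib, and combination with ablation or immunotherapy.
- Exclusions 3 and 4 concern drug hypersensitivity and incomplete laboratory results or data.
- Exclusions 7 and 8 concern tumour size above 10 cm and portal vein thrombosis.
- Exclusion 2 concerns other antibiotics in the 48 hours before TACE. It may remove some patients with an anastomosis, but only incidentally.
- Exclusion 9 may also remove some of them, if their ducts are dilated or the tumour has invaded the biliary tract.

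Count: 1 of 12 concerns the biliary tract, and 0 of 12 name an anastomosis.

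**3. Allocation and treatment**

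The lottery has two numbers, no stratification and 0 stated exceptions. The mention of local guidelines describes the ceftriaxone given to the antibiotic group; it creates no exception for the other group.

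**4. Following the rules for one patient**

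Take a patient aged 18 to 65 with hepatocellular carcinoma, receiving TACE at the centre, with a bilioenteric anastomosis, undilated ducts, no biliary invasion and none of exclusions 1 to 8. All three inclusions are met and no exclusion applies. Consecutive sampling brings the patient in, and the lottery can return 2. The patient then receives no antibiotic.

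**The case against.** The gap in the text is hard to dispute. The case on the other side concerns its weight.

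- **The group may not exist in this trial.** The documents do not say how many TACE patients at the centre have an anastomosis, and exclusions 2 and 9 may already remove some. This stands. The point rests on what the rules permit, not on a demonstrated number, and the count of 0 in 12 describes wording, not the size of a harm.
- **The mortality figure is general.** Quantifying harm would need the abscess risk of these patients with and without prophylaxis, and neither is given. This also stands. The figure is context only; the point rests on the cited recommendation.
- **The active arm may not be the prophylaxis the guideline intends.** The Introduction says that the choice of agent depends on the suspected pathogens, and the trial gives one dose of ceftriaxone. The documents do not settle this. It does not weaken the remedy: if the regimen is in doubt for these patients, that is a further reason to keep them out of the randomisation.
- **The guideline is seen only in paraphrase, and the evidence cited is mixed.** The strength of the recommendation cannot be checked here, and the Introduction cites studies pointing both ways. This limits certainty. However, the protocol itself reports the recommendation for high-risk patients as distinct from the advice on routine use.
- **The protocol need not follow the guideline.** Agreed: it nowhere says that eligibility does so, and the gap is therefore an omission, not a contradiction. A deliberate departure would still call for a stated reason, and none is given.
- **Clinicians would not enrol such a patient.** Perhaps so, but sampling is consecutive, and written criteria exist so that this does not depend on individual judgement.

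**Conclusion.** The concern holds. The protocol names two examples of high abscess risk for which its cited source recommends prophylaxis, and its criteria address one of them. As written, a patient with a bilioenteric anastomosis who meets no listed exclusion is eligible and can be allocated to no antibiotic.

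The omission is certain on the text. Its practical size is unknown: the number of such patients is not given and may be zero, and their abscess risk is not given either. For TACE in general the Introduction quotes an abscess incidence of 0.1 to 4.5%, but that cannot be applied to this group. The conclusion assumes that the Introduction reports the guideline fairly and that no unwritten screening rule keeps these patients out. The change should be made, because the possible harm to an individual is serious and the correction is small. Confidence in its practical importance is moderate.

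**What to change.** Add the presence of a bilioenteric anastomosis to exclusion 9, established from surgical history and from the CT already used for that item. If the sponsor means to enrol these patients, the protocol should say so and give the reason.

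The change governs only who may be randomised; it does not prescribe how excluded patients should be treated.

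The cost is one line in the eligibility list and one history question at screening. The drawback is that some screened patients, in unknown but possibly very small number, become ineligible, and the trial's result will then not apply to patients with an anastomosis.

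### Liver abscess is counted from imaging in an open-label trial, and nothing keeps the treatment arm from whoever reports the scan

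*Combined protocol and SAP*

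**What the plan says.** The title calls the trial "an open-label, randomised, prospective study". Under Sampling Technique, one group receives intravenous ceftriaxone and the other receives no antibiotic. No placebo is described. Allocation is drawn by the investigator: "In lottery method the investigator will randomly draw numbers from the box to choose sample until the final sample size reaches". Ceftriaxone is also local routine: "Current standard of care treatment at PKLI&RC (as per local guidelines) would be given to all patients receiving TACE for the intervention group".

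Under Study Outcomes, item 2 is "Occurrence of liver abscess as diagnosed by imaging within 30 days of the procedure". Item 3 is "Liver abscess requiring an intervention" in the same 30 days. The plan gives no imaging schedule or trigger, diagnostic criteria or masked reading for item 2, and no criterion for when an abscess requires intervention under item 3. It does not say who requests or reports the scans, or what they are told.

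The aim, at the end of the Introduction, names postoperative liver abscess as the event of interest. The Introduction states: "Incidence of liver abscess after TACE is 0.1 - 4.5" per cent.

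**The concern.** Randomisation balances the groups at entry. It does not balance who is scanned afterwards or how a scan is read. The group without antibiotic departs from the centre's routine, which is a plausible reason for closer attention to those patients, both in requesting a scan and in reading a borderline finding. The opposite imbalance is also possible, so the bias could create an apparent benefit or hide a real one.

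Abscess is the event in the study aim, and few are expected. A handful of differently detected cases could shift the result, and the planned data would not show whether that had happened.

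**Working it through.** The plan states no sample size, effect size or detection rate, so it has no figure to reproduce. What follows is an illustration.

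**Inputs.** From the documents: abscess risk 0.1-4.5% (Introduction); significance level 0.05, taken as two-sided (Statistical analysis, item 4); Fisher's exact or Pearson's chi-square test (item 2). Assumed: the detection probabilities, 200 or 400 patients per arm, and no false abscess calls.

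**1. Risk ratio.** Observed risk = true risk × detection probability, so

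observed RR = true RR × (detection with antibiotic ÷ detection without).

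| True RR | Detection, antibiotic | Detection, none | Observed RR |
|---|---|---|---|
| 1.0 | 65% | 95% | 0.65 ÷ 0.95 = 0.68 |
| 1.0 | 75% | 90% | 0.75 ÷ 0.90 = 0.83 |
| 1.0 | 45% | 90% | 0.45 ÷ 0.90 = 0.50 |
| 0.50 | 90% | 60% | 0.50 × 0.90 ÷ 0.60 = 0.75 |
| 0.50 | 90% | 45% | 0.50 × 0.90 ÷ 0.45 = 1.00 |
| any | equal | equal | unchanged |

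The baseline risk cancels, so these ratios hold anywhere in 0.1-4.5%.

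**2. False-positive rate.** True risk is equal in both arms and detection is 65% (antibiotic) against 95% (none). Every pair of event counts at 200 per arm was enumerated, and the probabilities of pairs with p < 0.05 were summed.

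| True risk | Observed risks | Mean expected events per arm | Pearson | Fisher |
|---|---|---|---|---|
| 4.5% | 2.925% v 4.275% | (5.85 + 8.55) ÷ 2 = 7.2 | 11.0% | 6.4% |
| 2% | 1.3% v 1.9% | (2.6 + 3.8) ÷ 2 = 3.2 | 6.8% | 2.4% |
| 1% | 0.65% v 0.95% | (1.3 + 1.9) ÷ 2 = 1.6 | 4.1% | 0.4% |
| 0.1% | 0.065% v 0.095% | (0.13 + 0.19) ÷ 2 = 0.16 | about 0 | about 0 |

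For comparison, equal detection of 80% at 4.5% risk gives 5.0% by Pearson. Other Pearson results at 4.5% risk:
- 65% v 95% at 400 per arm: 17.2%
- 45% v 90% at 200 per arm: 21.3%
- 75% v 90% at 200 per arm: 6.4%

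**3. Sensitivity to single cases.** With n per arm and m events in total, Pearson's statistic is (difference in counts)² × 2n ÷ [m(2n − m)]. At an assumed 200 per arm:
- 9 v 3: 36 × 400 ÷ (12 × 388) = 3.09, p = 0.079
- 10 v 3: 49 × 400 ÷ (13 × 387) = 3.90, p = 0.048

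One extra case crosses 0.05 by Pearson. It does not by Fisher: given 13 events, twice the hypergeometric probability of 3 or fewer in one arm is 0.087.

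**The case against.** **Readers may not know the arm.** A reader might infer from the open-label design that those who request and read the scans know the allocation. The documents do not say so. They show only that the investigator who draws the number knows it. This stands, and it limits the point to the lack of any safeguard.

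**The error rates depend on the corner chosen.** A reader might take 11% or 21% as the general size of the problem. Those figures need 4.5% true risk, Pearson's test and a large gap in detection. At 2% risk about 3 events per arm are expected, Fisher's test would normally apply, and its rate is 2.4%. For 75% v 90% at 4.5% risk, the gain over equal detection is 6.4 − 5.0 = 1.4 percentage points. This stands too. The ratio distortion remains at every risk, but its size simply restates the assumed detection rates.

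**The model is partial.** It covers missed abscesses, not over-called ones. False calls would add to the observed risk rather than multiply it. It also does not separate scanning from reading, so the gain from masking the reader alone is not quantified.

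**Masking the reader leaves the main route open.** Imaging diagnosis is less subjective than clinical judgement. The more exposed steps are who is scanned and who has an intervention, and both stay with an unmasked team. That is correct, and is why the number imaged in each arm must be reported as well.

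**Tying outcome 3 to a masked report could lose true events.** A drained, genuine abscess with an equivocal report would be discarded. The fix therefore does not do this.

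**Conclusion.** The point holds as a gap in outcome ascertainment. The trial is open-label, its key event depends on a scan being requested and read, and no provision keeps the arm from the reader. It is not shown that readers know the arm, that bias will occur, or which way it would run.

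If detection does differ, the risk ratio is distorted by the ratio of detection probabilities at any abscess risk, in either direction. A false-positive rate above 5% appears only towards the top of the cited range: for 65% v 95% at 200 per arm, at 2% and 4.5% risk with Pearson's test, and among the risks examined only at 4.5% with Fisher's. All of this rests on assumed detection rates and sample sizes and on no false abscess calls. The change is worth making because it is cheap and because, without it, neither a positive nor a null abscess result can be separated from a difference in looking.

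**What to change.** Add to Study Outcomes:

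- Allocation and ceftriaxone are left off the post-TACE imaging request.
- Outcome 2 is taken from the report of a radiologist not told the arm: where available, an existing radiologist who did not perform that patient's TACE.
- The number of patients imaged by day 30 is reported for each arm, with the timing of and reason for imaging.
- Outcome 3 stays as defined, and the number of outcome 3 events without a masked imaging diagnosis is reported.

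This sets no rule for when to scan or intervene; those decisions stay with the centre.

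The cost is a change to the request form, a few sentences in the protocol and a few recorded items per patient. No extra scan or visit is needed. The low cost assumes that a radiologist other than the operator already reports these scans, which the documents do not say. If the operator reports them, another reader is needed. The remaining weakness is that the treating team still knows the arm, so the decisions to scan and to intervene stay unmasked. The counts by arm would show a difference in imaging but would not correct for it.

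### Forward stepwise logistic regression reports odds ratios and confidence intervals for variables picked on the same data, with no allowance for selection and no limit tied to the number of events

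*Combined protocol and SAP*

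**What the plan says.** Statistical analysis, item 3, builds the model in three moves.

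- Candidates are "Significant variables (P < 0.01) in univariate analysis and covariates considered clinically influential". The second group is not listed and need not pass the screen.
- Both groups "were then analyzed by multivariate stepwise logistic regression (forward stepwise logistic regression) to identify significant variables". No entry or removal criterion is given. Nothing says that treatment arm or any other term is forced in.
- Logistic models then give odds ratios and 95% intervals for whatever proved significant. The text describes these as "variables for finding potential risk factors in WBC> 11×10^9 /L group or postoperative infection group". The dependent variable is therefore leukocytosis or postoperative infection, and the latter is not defined.

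Item 4 gives the general threshold: a P "value less than 0.05 was considered statistically significant". The software is SPSS version 24, and no penalised or exact method is named. There is no cap on the number of terms, no plan for separation and no correction for selection.

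The only numerical event rate is in the Introduction: "Incidence of liver abscess after TACE is 0.1 - 4.5" per cent. The Introduction calls post-procedure infection uncommon without giving a figure, and no rate is given for a white cell count above 11 × 10^9/L. Sampling Technique refers to a final sample size but does not state it.

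**The concern.** Two faults are in play, and they reach differently far.

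**Selection.** A variable is reported because its estimate was large relative to its error. Its odds ratio is then biased away from 1, and a 95% interval computed as if the model had been fixed in advance loses its stated coverage. The open-ended clinically influential route weakens the one safeguard present, the 0.01 screen. Those covariates can also be dropped again on a P value, because they too go through the stepwise procedure.

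**Sparse data.** If events are few, a binary factor may have no events in one of its levels. An ordinary logistic fit then has no finite odds ratio.

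At stake are the published risk factors. Readers could use them to decide which patients are thought to need prophylaxis.

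**Working it through.** The plan states no sample size, event count or power, so there is no figure of its own to reproduce.

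**Inputs from the plan.** Screen at P < 0.01; unlisted covariates that bypass it; forward stepwise selection; significance level 0.05; abscess incidence 0.1–4.5%.

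**Assumptions.** N = 200; eight candidates (four binary at 30% prevalence, four standard normal); entry at P < 0.05, two-sided; ordinary maximum-likelihood fit. For scale, the Introduction names seven risk factors for infection after TACE, and treatment arm would make eight.

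**1. Expected abscesses, N × rate.**

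| N | 0.1% | 2% | 4.5% |
|---|---|---|---|
| 100 | 0.1 | 2 | 4.5 |
| 200 | 0.2 | 4 | 9 |
| 500 | 0.5 | 10 | 22.5 |
| 1000 | 1 | 20 | 45 |

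These are abscess counts. Counts for leukocytosis cannot be derived from the documents.

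**2. Chance of at least one false risk factor when no candidate matters.** With independent candidates, of which s are screened and b bypass the screen, this is approximately 1 − 0.99^s × 0.95^b.

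| Eight candidates | Formula | Result | Simulated, N = 200 |
|---|---|---|---|
| All screened | 1 − 0.99^8 | 7.7% | about 5–9% |
| Half bypass | 1 − 0.99^4 × 0.95^4 | 21.8% | about 22–32% |
| All bypass | 1 − 0.95^8 | 33.7% | about 34–38% |

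The simulated ranges cover event rates from 2% to 30%. A separate simulation with 12 candidates gave 9–14%, 27–32% and 43–48%; the formula gives 11.4%, 30.8% and 46.0%. The rates hardly moved between 4 and 60 events, so this fault does not depend on rarity.

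**3. Size and coverage of what is reported** (eight candidates, all bypassing, 600 trials per setting).

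- No real effect: the median selected odds ratio was 9.8 at 2% incidence, 4.9 at 4.5% and 2.4 at 15%.
- One binary factor with true odds ratio 2: it was selected in 21% of trials at 4.5% incidence and 43% at 15%. When selected, its median odds ratio was 5.3 and 2.95. The nominal 95% interval covered the truth about 90% of the time.
- Selected noise variables (12-candidate simulation): the interval contained the true value of 1 in only 0–38% of cases. This follows almost by construction, since selection requires a test against 1 to reject.

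**4. Infinite odds ratios.** For a factor with 20% prevalence, the chance that all n events fall in one level is 0.8^n + 0.2^n: 33% at n = 5, 13% at n = 9, 4.4% at n = 14 and 1.2% at n = 20. In the eight-candidate simulations at 2–4.5% incidence, about 12–17% of trials ended with an infinite odds ratio when all candidates bypassed the screen, and 0.3–2% when all were screened. At 15% or more the share was 0–0.2%. The 12-candidate simulation left a little more at 20% incidence: 45.7% of trials kept a variable and 3.3% of those models were separated, so 0.457 × 0.033 = 1.5% of trials.

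**5. Does removing selection suffice?** A fixed three-term model (arm, one continuous and one binary covariate; true treatment odds ratio 1), fitted by ordinary maximum likelihood:

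| N, rate | Expected events | Some odds ratio infinite |
|---|---|---|
| 200, 2% | 4 | 52% |
| 100, 4.5% | 4.5 | 45% |
| 200, 4.5% | 9 | 17% |
| 300, 4.5% | 13.5 | 6.7% |
| 200, 10% | 20 | 1.4% |
| 200, 20% | 40 | 0.1% |

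Firth fits stayed finite in all of these settings, with 95–99.9% coverage for treatment (Wald intervals). With few events, prespecification alone is not enough.

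**The case against.** The strongest reply is that the abscess rate does not belong to this regression. Item 3 models leukocytosis or postoperative infection; it does not name abscess, unless the undefined infection group includes it. Leukocytosis may be common: at 20% of 200 there would be 40 events, and separation would be rare. This stands. A reader might infer that the plan is bound to fit its model to a handful of events and print infinite odds ratios, but the documents give neither the sample size nor the relevant rate.

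Second, the plan does have a screen. If every candidate must pass P < 0.01, a false risk factor appears in only about 5–9% of trials. This also stands: the figure above one third is the all-bypass worst case. But the bypass list is open, so the lower figure cannot be relied on either.

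Third, the intervals might be called too narrow. In absolute terms they are not. With 4–5 events, the ordinary interval for treatment in the fixed model had an upper-to-lower ratio of about 50, and without selection coverage was about 95% or more. The defect is only that the intervals ignore selection.

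Fourth, the plan calls these potential risk factors, and maximum likelihood is inferred from ordinary logistic regression in SPSS. Both are fair. Tentative wording, however, does not correct the estimates printed beside it.

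**Conclusion.** The selection fault holds at any event rate: reported odds ratios are exaggerated, and their intervals make no allowance for how the variables were chosen. The chance of at least one false risk factor runs from about 5–9% to about 34–38%, depending mainly on how many covariates bypass the screen. These figures rest on eight independent null candidates, N = 200 and entry at 0.05.

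The sparse-data fault is conditional on a rare modelled outcome. It matters at rates like those quoted for abscess and essentially disappears at 15% or more.

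A reader might also infer that the randomised comparison is compromised. Item 3 is a search for risk factors, and the fault on its face affects those claims only; whether the plan contains an adequate comparison by arm is a separate question. The change is worth making before analysis, but this point alone does not threaten the trial's main purpose.

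**What to change.** Rewrite item 3 as follows.

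- Delete the univariate screen as a route into the model, and delete the stepwise step.
- Define postoperative infection, and name the outcome of each model with its expected number of events.
- Prespecify a short list: treatment arm plus a few factors that the Introduction already names, such as hepatic function or albumin, and diabetes. Force in every term and report every term, significant or not.
- State beforehand how the number of terms depends on the events observed. For very sparse outcomes, give single-factor estimates only.
- When events are few, use Firth penalised or exact logistic regression, with profile-likelihood intervals for the Firth fit. Otherwise an ordinary fit of the fixed model is enough. For a three-term model, the fixed-model results above put the changeover at roughly 20 to 40 events.
- Label all risk-factor results exploratory.

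The cost is a paragraph of SAP text and a short script outside SPSS, with no change to trial conduct. The price is fewer independent risk factors to report.
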